### 3.7.1. Schedule of Assessments

#### 3.7.1.1. Screening

The screening period begins after written informed consent has been obtained. Subjects will participate in screening activities for 2 days to 42 days. The screening period may be extended after discussion with and approval by the medical monitor. After the ICF has been signed, the site will obtain a Subject identification/identifier (ID) by accessing the IVRS or IWRS. Completion of screening activities may require more than 1 visit; however, only the initial visit will be registered in the IVRS or IWRS.

Screening evaluations will include the following:

- At the time of the subject's screening visit, the caregiver will be provided a document that will outline all caregiver responsibilities and their role in this trial. The caregiver should acknowledge and agree to undertake all the tasks designated by this protocol at the time of the informed consent process.
- Trial personnel will call the IVRS or access the IWRS to register the visit (initial screening visit only).
- The investigator must assess the capacity of the subject to provide informed consent during the screening period. Once this determination is made by the investigator, the options for obtaining informed consent from and/or on behalf of the subject must be followed as provided in [Section 3.4.1](#).
- An assessment of all inclusion and exclusion criteria will be made to determine the subject's eligibility for the trial.
- Demographic data will be recorded.
- A general clinical evaluation will be performed, including concurrent medical conditions, medical history over the past 2 years, and medical history beyond 2 years that is considered to be clinically relevant per the investigator's judgment.
- Psychiatric and neurological history will be recorded.
- If a previous MRI or CT scan of the brain performed after the onset of symptoms of dementia is not available, then an MRI/CT scan of the brain should be performed during screening. In addition, a repeat MRI/CT scan of the brain may be requested to be performed CCI in order to confirm eligibility.
- Medications taken within 30 days of screening (signing of ICF/assent) will be recorded.
- Washout from prohibited concomitant medications will begin, if applicable (see [Section 4.1](#)).
- A complete physical examination (including height and waist circumference) will be performed.

Protocol 331-12-284

- A detailed neurological examination, which will consist of an evaluation of the subject's mental status, cranial nerves, motor system (eg, motor strength, muscle tone, reflexes), cerebellar system (eg, coordination), gait and station, and sensory system, will be performed by a physician.
- Vital sign measurements (body weight, body temperature, blood pressure, and heart rate) will be recorded. Blood pressure and heart rate are to be measured in the following order: supine, sitting, and standing. Blood pressure and heart rate measurements in the supine position should be taken after the subject has been lying for at least 5 minutes. The sitting and standing measurements should be taken within 1 to 3 minutes of changing positions. See [Section 3.4.3](#) for exclusions based on outcome of screening vital sign measurements. Vital signs are to be completed before any blood is drawn.
- A standard 12-lead ECG will be performed after the subject has been supine and at rest for at least 5 minutes. Subjects with screening QTcF  $\geq 450$  msec (males) or  $\geq 470$  msec (females) will be excluded from the trial, unless due to ventricular pacing (see [Section 3.7.4.4](#)). Abnormal results for ECGs should be repeated once at screening with 3 consecutive ECG recordings to ensure reproducibility of the abnormality before excluding a subject. The ECG is to be completed before any blood is drawn.
- Blood samples will be drawn for the presence of hepatitis B surface antigen (HBsAg) and antibodies to hepatitis C (anti-HCV). Subjects with a positive result for any of these tests will be excluded from the trial. Vital sign and ECG assessments should be completed before any blood samples are collected.
- Blood samples will be collected for clinical laboratory tests (hematology, including PT, aPTT, and INR, and serum chemistry, including prolactin [blinded], HbA1c, ACTH, cortisol, and TSH with reflex to free T4 if the result for TSH is abnormal) and should be obtained after a minimum 8-hour fast, if possible. See [Section 3.7.4.2](#) for exclusions based on outcome of screening clinical laboratory tests. Vital signs and ECG assessments should be completed before any blood samples are collected.
- Samples will be obtained for blood alcohol testing. Subjects with a positive blood alcohol test at screening may be retested or rescreened once for participation in the trial with consent of the medical monitor.
- Urine will be collected from all potential subjects for urinalysis and urine screen(s) for drugs of abuse. Subjects positive for cocaine, marijuana, or other illicit drugs are not eligible to be retested or rescreened. Subjects with a positive drug screen resulting from use of prescription or OTC medications or products may be retested (the evaluation may be repeated within the screening period) or rescreened once for participation in the trial after consent of the medical monitor.
- Urine albumin-to-creatinine ratio (ACR) will be determined only for subjects with insulin-dependent diabetes mellitus (IDDM) (must be  $< 30$  mg/g; calculated as urine albumin [mg/dL]/urine creatinine [g/dL]).

Protocol 331-12-284

- A urine pregnancy test will be performed for all women of childbearing potential. All positive results must be confirmed by a serum pregnancy test. Subjects with positive urine and serum test results will be excluded from the trial.
- An adequately trained and experienced clinician will confirm the diagnosis of probable Alzheimer's disease using the NINCDS-ADRDA criteria.
- An adequately trained and experienced physician who performs the neurological examination will complete the Hachinski Ischemic Scale (Rosen Modification).
- A qualified and certified rater will administer the CMAI and NPI-NH (for institutionalized subjects) or NPI/NPI-NH (for non-institutionalized subjects) to the identified caregiver.
- An adequately trained and experienced clinician will administer the CGI-S.
- An adequately trained and experienced clinician will administer the MMSE.
- CCI [REDACTED]
- AEs will be recorded, beginning with the signing of the ICF.
- Concomitant medications will be recorded.
- CCI [REDACTED]
- The subject's caregiver and/or facility staff will complete a paper diary daily (if possible) after the ICF is signed, continuing through Week 12/ET.

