## 2. Trial Rationale and Objectives

### 2.1. Trial Rationale

Behavioral symptoms, such as agitation, are core features in subjects with Alzheimer's disease and related dementias and develop in the majority of dementia subjects. The presence of agitation in subjects with Alzheimer's disease places a significant burden not only on subjects and their caregivers but also on the healthcare system.

Based on the data available from atypical antipsychotics in the treatment of agitation or aggression in Alzheimer's disease, brexpiprazole is an appropriate candidate to evaluate the benefit-risk ratio of this class of drugs in this subject population in today's clinical setting. In addition to potential treatment effects, the receptor binding profile of brexpiprazole may confer additional benefits in terms of the safety profile, particularly with respect to hyperprolactinemia, sleep quality, and weight gain.

In light of the Food and Drug Administration (FDA) boxed warning of increased mortality with the use of antipsychotics in elderly subjects with dementia-related psychosis and similar caution advised by other regulatory authorities, the clinical trial will be conducted in an environment that allows for close safety monitoring, in subjects who are living in either an institutionalized setting or in a non-institutionalized setting where the subject is not living alone and has a caregiver who can spend a minimum of 2 hours per day for 4 days per week with the subject in order to assess changes in the subject's condition. Furthermore, a slow titration schedule will be implemented with brexpiprazole being titrated to the highest assigned dose (2 mg/day) over a 4-week period. CCI

[REDACTED]

[REDACTED]

[REDACTED]

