Neurological examination l	X								X			
Vital signs m	X	X	X	X	X	X	X	X	X			
Clinical laboratory tests (hematology, serum chemistry, urinalysis) n	X	X o			X p		X p		X			
Prolactin (blinded) n	X								X			
TSH with reflex to free T 4 if abnormal n	X								X			
HbA 1c n	X								X			
PT, aPTT, and INR n	X								X			
ACTH and cortisol n	X								X			
Urine pregnancy test (women of childbearing potential) only q	X								X			
ECG r	X	X			X		X		X			
Blood alcohol s,t	X											
Urine drug screen s,t	X											
MMSE	X	X							X			

Protocol 331-12-284

Table 3.7-1 Schedule of Assessments											
Assessment	Visit										
	Screening a	Baseline (Day 0)	Day 3	Wk 2	Wk 4	Wk 6	Wk 8	Wk 10	Wk 12/ ET b	FU c	■ d
CCI		■		■	■		■		■		
■		■		■	■		■		■		
Adverse events v	X	X	X	X	X	X	X	X	X	X	
Pharmacokinetic sampling w		X					X		X		
■		■									
Concomitant medications y	X	X	X	X	X	X	X	X	X	X	
■											■
OTHER PROCEDURES											
Register trial visit in IVRS/IWRS	X	X	X	X	X	X	X	X	X		
Randomize eligible subjects via IVRS/IWRS		X									
IMP dispensing aa		X	X	X	X	X	X	X			
IMP accountability			X	X	X	X	X	X	X		
Telephone contact bb											
ADDITIONAL ENTRANCE/HISTORY											
MRI/CT scan cc	X cc										

ACTH = adrenocorticotrophic hormone; AIMS = Abnormal Involuntary Movement Scale; anti-HCV = hepatitis C antibodies; aPTT = activated partial thromboplastin time CCI

CGI-S = Clinical Global Impression-Severity of Illness; CMAI = Cohen-Mansfield Agitation Inventory; CCI

[figure not shown]

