### 3.7.1.2. Baseline (Day 0)

If the subject is found to be eligible for the trial during the screening period, the following procedures will be performed at the baseline visit:

- CCI [REDACTED]
- Inclusion and exclusion criteria will be verified.
- The investigator must assess the capacity of the subject to provide informed consent throughout the course of the trial. Once this determination is made by the investigator, the options for obtaining informed consent from and/or on behalf of the subject must be followed as provided in [Section 3.4.1](#).
- A qualified and certified rater will administer the CMAI and NPI-NH (for institutionalized subjects) or NPI/NPI-NH (for non-institutionalized subjects) to the identified caregiver.
- An adequately trained and experienced clinician will administer the CGI-S.
- CCI [REDACTED]

Protocol 331-12-284

- CCI [REDACTED]
- [REDACTED]
- An adequately trained and experienced clinician will administer the MMSE.
- CCI [REDACTED]
- [REDACTED]
- Vital sign measurements (body weight, body temperature, blood pressure, and heart rate) will be recorded. Blood pressure and heart rate are to be measured in the following order: supine, sitting, and standing. Blood pressure and heart rate measurements in the supine position should be taken after the subject has been lying for at least 5 minutes. The sitting and standing measurements should be taken within 1 to 3 minutes of changing positions. Vital signs are to be completed before any blood is drawn.
- Blood samples will be collected for clinical laboratory tests (hematology and serum chemistry) and should be obtained after a minimum 8-hour fast, if possible. Urine will be collected for urinalysis. If a fasting blood sample was obtained at the screening visit and less than 14 days have elapsed since the screening visit, clinical laboratory tests (hematology, serum chemistry, and urinalysis) do not need to be repeated at the baseline visit. Vital signs and ECG assessments should be completed before any blood samples are collected.
- A standard 12-lead ECG will be performed after the subject has been supine and at rest for at least 5 minutes. The ECG is to be completed before any blood is drawn.

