- A fasting blood draw will be collected for clinical laboratory tests (hematology, including PT, aPTT, and INR; and serum chemistry, including prolactin [blinded] HbA1c, ACTH, cortisol, and TSH with reflex to free T4 if the result for TSH is abnormal) and urine will be collected for urinalysis. Vital sign and ECG assessments should be completed before any blood samples are collected.
- A blood sample will be obtained for pharmacokinetic analysis. The date and time of the blood draw and the date and time of the last 2 doses of IMP prior to the blood draw will be recorded on the eCRF. Vital sign and ECG assessments should be completed before any blood samples are collected.
- CCI [REDACTED]
- Women of childbearing potential will be given a urine pregnancy test. Any positive result must be confirmed by a serum pregnancy test.
- AEs and concomitant medications will be recorded.
- Diary recording will be stopped.
- Final IMP accountability will be performed.

Protocol 331-12-284

- Trial personnel will call the IVRS or access the IWRS to register completion or discontinuation from the trial.

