## 9 Safety Analysis

Standard safety variables to be analyzed include AEs, clinical laboratory tests, vital signs, ECGs, body weight, waist circumference and physical examination. In addition, data from the following safety scales will be evaluated: MMSE score, CCI [REDACTED]

[REDACTED]  
[REDACTED]  
[REDACTED]  
[REDACTED]  
[REDACTED]

Safety analysis will be conducted based on the Safety Sample. In general, baseline of a safety variable is defined as the last observation of the variable before taking the first dose of IMP, unless specified otherwise.

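### The prolactin baseline is a screening value that may predate antipsychotic washout, which can lower the reported change in both arms and add noise, without biasing the arm difference

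*Protocol*

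**What the plan says.** - **When prolactin is drawn.** In the Schedule of Assessments (Protocol Table 3.7-1) prolactin has its own row, marked at Screening and Week 12/ET only. The visit text agrees. Section 3.7.1.1 lists "hematology, including PT, aPTT, and INR, and serum chemistry, including prolactin [blinded" at screening, and 3.7.1.4 names prolactin again at Week 12/ET. For Day 0, section 3.7.1.2 says "Blood samples will be collected for clinical laboratory tests (hematology and serum chemistry) and should be obtained after a minimum 8-hour fast, if possible", without naming prolactin. These Day 0 tests may be skipped if a fasting screening sample is less than 14 days old.
- **When washout happens.** The same list of screening procedures says "Washout from prohibited concomitant medications will begin, if applicable". Table 4.1-1 asks for a 7-day washout of antipsychotics, with separate, generally longer rules for clozapine and depot products. Screening lasts 2 to 42 days, can be extended, and may need more than one visit.
- **Who may enter.** Exclusion criterion 4 removes only subjects with insufficient response to two or more antipsychotics, so recent users can be enrolled.
- **How prolactin is analysed.** SAP section 9 states that in general "baseline of a safety variable is defined as the last observation of the variable before taking the first dose of IMP". SAP 9.2.1 gives means and mean changes for prolactin by treatment and visit. SAP 9.2.2 gives the incidence of treatment-emergent potentially clinically relevant values by arm; Appendix 1 sets the prolactin criterion at above ULN.
- **Why it is of interest.** Protocol 2.1 says the drug's receptor profile "may confer additional benefits in terms of the safety profile, particularly with respect to hyperprolactinemia, sleep quality, and weight gain".

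**The concern.** A baseline should describe the subject without the effect of a drug that is about to be stopped. Nothing ties the screening prolactin draw to the end of washout. Someone who arrives on a prolactin-raising antipsychotic can therefore have a raised baseline, and prolactin would fall by Week 12 simply because that antipsychotic was stopped. The protocol recognizes that antipsychotics differ here: section 1.1.1 contrasts the drug with risperidone on prolactin in an animal model.

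Two planned outputs use this baseline. The mean change by arm would mix study treatment with recovery from earlier treatment. The treatment-emergent count could drop subjects who were already above ULN at screening. Hyperprolactinemia is named in the rationale as a possible advantage of the drug, so the figures should be readable at face value.

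**Working it through.** The plan gives no prolactin figure to reproduce. The check has two parts: tracing the passages, and an illustration on assumed inputs.

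**1. Does a Day 0 chemistry draw include prolactin?** Table 3.7.4.2-1 lists prolactin under serum chemistry, which could suggest that it does. But the schedule marks chemistry at Baseline and at Weeks 4 and 8 and leaves the prolactin row blank at all three. The Amendment 3 summary confirms that prolactin was removed at Weeks 4 and 8 while chemistry stayed. On the current text, then, a chemistry draw does not imply prolactin, and the last pre-dose value is the screening one. The table and the schedule still need reconciling.

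**2. Can that value reflect an earlier antipsychotic?** Yes. Washout starts after consent, within screening, and no passage orders the blood draw after it.

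**3. Illustration of mean change.** None of these inputs is in the documents:
- unmedicated prolactin log-normal, median 9 ng/mL, log-SD 0.45
- within-subject log-SD 0.2
- share *f* on an antipsychotic at the screening draw, with prolactin tripled
- study drug multiplies prolactin by 1.3, placebo by 1.0

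Mean unmedicated level = 9 × exp(0.45²/2) × exp(0.2²/2) ≈ 10.16. The excess in an affected subject is (3 − 1) × 10.16 = 20.3.

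Mean change on drug = 0.3 × 10.16 − *f* × 20.3. Mean change on placebo = 0 − *f* × 20.3.

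| *f* | Drug | Placebo | Difference |
|---|---|---|---|
| 0% | +3.0 | 0.0 | +3.0 |
| 10% | +1.0 | -2.0 | +3.0 |
| 20% | -1.0 | -4.1 | +3.0 |
| 40% | -5.1 | -8.1 | +3.0 |

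The term *f* × 20.3 is the same in both arms and cancels. The Week 12 means, about 13.2 and 10.2, do not depend on *f*.

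**4. Noise.** Simulating the same inputs, the SD of change on drug rises from 4.0 at *f* = 0 to 10.2 at *f* = 20%. With 130 per arm and complete data, the 95% half-width for the difference in change grows from about 0.9 to 2.5 ng/mL.

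**5. Treatment-emergent above ULN, if a non-elevated baseline is required.** Let *q* be the chance that an affected subject is above ULN at screening. Subjects masked per arm = 130 × *f* × *q*. If Week 12 status is independent of screening status, the share of the count kept is 1 − *f* × *q*.
- *f* = 10%, *q* = 30%: 130 × 0.03 = 3.9 masked, 97% kept.
- *f* = 20%, *q* = 50%: 13 masked, 90% kept. True counts of 26 and 13 become 23.4 and 11.7.
- *f* = 40%, *q* = 70%: 130 × 0.28 = 36.4 masked, 72% kept.

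The ratio between arms is unchanged. The simulation, with an assumed ULN of 20 ng/mL and *f* = 20%, gives 7.5% instead of 9.4% on drug, and a drug-to-placebo ratio of about 3.9 in either case.

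**The case against.** The strongest reply is that the trial is randomized and placebo-controlled and SAP 9.2.1 tabulates both arms. Prior antipsychotic use is spread evenly in expectation, so placebo falls by as much as drug does and the contrast is unbiased. SAP 9.2.1 also already plans Week 12 means by arm, which do not use the baseline. Both points stand. Three stronger readings are tempting, and the documents do not support them.

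- **That the sign of the drug effect is reversed.** The figure of -1.0 instead of +3.0 is the drug arm alone, under assumed inputs. The placebo figure of -4.1 beside it shows the effect intact.
- **That every subject on an antipsychotic is sampled before washout.** Screening may take several visits and no passage fixes the order, so some draws may fall during or after washout.
- **That the SAP necessarily undercounts new elevations.** It does not define treatment-emergent for laboratory values, and the Appendix 1 prolactin criterion carries no baseline condition, whereas the hematocrit criterion does. If any post-dose value above ULN counts, nothing is lost, though old and new elevations cannot be told apart.

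It is also fair that prolactin is descriptive: SAP 9.2.1 states no between-arm test, SAP 9.1 does not list it among adverse events of special interest, and it appears in the rationale but not the objectives.

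What remains is that the by-arm changes can mislead when read within an arm, and that the comparison of changes is noisier than it needs to be.

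**Conclusion.** The point holds in limited form. The schedule makes a screening value the prolactin baseline, and that value can carry the effect of an earlier antipsychotic. The within-arm mean change can be pulled down in both arms, and the comparison of changes loses precision. New values above ULN are undercounted only under one reading of an undefined term.

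The size is unknown, because the documents do not say how many subjects come off a prolactin-raising antipsychotic or how far their levels are raised. The figures above are illustrations and must be read with both arms together. A reader might infer that the plan would produce a false prolactin advantage over placebo; randomization rules that out in expectation. This is a cheap improvement to consider for a descriptive safety parameter, not a threat to the trial's conclusions.

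**What to change.** 1. **Protocol.** Where blood is already drawn at Day 0, add prolactin to that sample and use it as baseline. Subjects whose Day 0 tests are skipped under the 14-day provision keep the screening value, so flag the baseline source in the data and tables. Reconcile Table 3.7.4.2-1 with the prolactin row of Table 3.7-1.
2. **SAP 9.2.1 and 9.2.2.** Add the proportion above ULN at Week 12/ET by arm regardless of baseline; the Week 12 means are already planned. State whether treatment-emergent requires a non-elevated baseline. Show change and values above ULN by antipsychotic use at screening, taken from the medications already recorded for the 30 days around screening.

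The cost is one analyte on an existing sample, a short amendment, and a few table panels. The drawback is that Day 0 and screening baselines will be mixed, and the flag is needed for that reason. If the amendment is not practical, item 2 can be done alone without new samples.

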### 3.7.1.2. Baseline (Day 0)

If the subject is found to be eligible for the trial during the screening period, the following procedures will be performed at the baseline visit:

- CCI [REDACTED]
- Inclusion and exclusion criteria will be verified.
- The investigator must assess the capacity of the subject to provide informed consent throughout the course of the trial. Once this determination is made by the investigator, the options for obtaining informed consent from and/or on behalf of the subject must be followed as provided in [Section 3.4.1](#).
- A qualified and certified rater will administer the CMAI and NPI-NH (for institutionalized subjects) or NPI/NPI-NH (for non-institutionalized subjects) to the identified caregiver.
- An adequately trained and experienced clinician will administer the CGI-S.
- CCI [REDACTED]

Protocol 331-12-284

- CCI [REDACTED]
- [REDACTED]
- An adequately trained and experienced clinician will administer the MMSE.
- CCI [REDACTED]
- [REDACTED]
- Vital sign measurements (body weight, body temperature, blood pressure, and heart rate) will be recorded. Blood pressure and heart rate are to be measured in the following order: supine, sitting, and standing. Blood pressure and heart rate measurements in the supine position should be taken after the subject has been lying for at least 5 minutes. The sitting and standing measurements should be taken within 1 to 3 minutes of changing positions. Vital signs are to be completed before any blood is drawn.
- Blood samples will be collected for clinical laboratory tests (hematology and serum chemistry) and should be obtained after a minimum 8-hour fast, if possible. Urine will be collected for urinalysis. If a fasting blood sample was obtained at the screening visit and less than 14 days have elapsed since the screening visit, clinical laboratory tests (hematology, serum chemistry, and urinalysis) do not need to be repeated at the baseline visit. Vital signs and ECG assessments should be completed before any blood samples are collected.
- A standard 12-lead ECG will be performed after the subject has been supine and at rest for at least 5 minutes. The ECG is to be completed before any blood is drawn.
- Blood samples will be obtained for pharmacokinetic analysis. If blood samples for clinical laboratory tests are not collected at the baseline visit, pharmacokinetic samples do not need to be obtained at baseline. Vital sign and ECG assessments should be completed before any blood samples are collected.
- CCI [REDACTED]
- AEs and concomitant medications will be recorded.

Protocol 331-12-284

- Trial personnel will call the IVRS or access the IWRS to randomize the subject and obtain a blister card assignment.
- Diary recording will continue.
- The subject will take the first dose of the IMP from the assigned blister card on Day 1 (ie, the day after the baseline visit). The subject should take the IMP at approximately the same time each day, preferably in the morning, without regard to meals.

